## 5.4 Time and Events Table

\* Bone scan performed every 8 weeks only if bone lesions present in baseline bone scan.

@ optional

# Immunologic blood collection is needed at baseline, post SABR, post HD IL-2, at 8 week, six months and at 1 year

& Comprehensive chemistry will be done once a year, after this point.

% Cost and Convenience Questionnaire will only be administered at the first follow up. All other QoL surveys will take place every other follow-up.

1 Additional procedures, ICU admission, and lab requirements may apply in association with IL-2 administration, as detailed in appendix C.

^ if previous biopsy of metastatic site within six months with adequate review of slides is not available. If the patient participated in protocols [such as the Urology Tissue Repository Protocol (STU 032011-187)] or procedures where tissue confirming kidney cancer diagnosis was collected and the biopsy in storage is still available, the study team may request a tissue sample.

## 5.5 Removal of Subjects from Study

Subjects can be taken off the study treatment and/or study at any time at their own request, or they may be withdrawn at the discretion of the investigator for safety, behavioral or administrative reasons. The reason(s) for discontinuation will be documented and may include:

- 5.5.1 Subject voluntarily withdraws from treatment (follow-up permitted);
- 5.5.2 Subject withdraws consent (termination of treatment and follow-up);

5.5.3 Subject is unable to comply with protocol requirements; patients must be withdrawn from the trial and replaced if they failed to receive at least one cycle of HD IL-2

- 5.5.4 Subject demonstrates disease progression (unless continued treatment with HD IL-2 is deemed appropriate at the discretion of the medical oncologist);
- 5.5.5 Subject experiences toxicity that makes continuation in the protocol unsafe;
- 5.5.6 Treating physician judges continuation on the study would not be in the subject's best interest;
- 5.5.7 Subject becomes pregnant (pregnancy to be reported along same timelines as a serious adverse event);
- 5.5.8 Development of second malignancy (except for basal cell carcinoma or squamous cell carcinoma of the skin) that requires treatment, which would interfere with this study;
- 5.5.9 Lost to follow-up.

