## 2.2 Secondary Objectives

- **2.2.1** To evaluate the overall survival (OS), which is defined as the time between date of registration and the date of death due to any cause. In analyzing the OS, it is important to take into account the MSKCC prognostic criteria defined by Motzer et. al. mRCC patients and compare the outcome in the appropriate risk categories [90].
- **2.2.2** To evaluate progression free survival (PFS), which is defined as the time between date of registration and the first date of documented disease progression or date of death due to any cause.
- **2.2.3** To evaluate time to progression (TTP), which is defined as time between date of registration and date of documented progression.
- **2.2.4** To evaluate the local control rate of irradiated lesions.
- **2.2.5** To evaluate median response duration, which is defined as the time between the date a response (CR or PR) was first seen until date of progression.
- **2.2.6** To measure treatment-related tumor-specific immune response.
- **2.2.7** To evaluate the tolerability and toxicity of this regiment as measured according to CTCAE v4.0.
- **2.2.8** To measure the improvement in health-related quality of life (HRQoL).

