## 4.2.1 Treatment Dosage and Administration

HD IL-2 will be administered at a dose of 600,000 IU/kg every 8h for a total of up to 14 doses (considered as one cycle), followed by a one week break and then another cycle of the same dose over another week. Each HD IL2 course consists of two cycles of up to 14 doses each separated by a week of rest. A total of three courses may be administered for patients without progression at the discretion of the medical oncologist. Patients will be admitted to the ICU of the corresponding hospital for IL-2 treatment and close monitoring according to the HD IL-2 algorithm (appendix B). Patients will undergo placement of a central venous catheter, typically a PICC line, before each course of therapy.

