## 4.5 Removal of Subjects from Protocol Therapy

Subjects will be removed from therapy when any of the criteria listed in Section 5.5 apply, however will continue to be followed up as per protocol described above. Notify the Principal Investigator, and document the reason for study removal and the date the subject was removed in the Case Report Form.

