#### 5.1.18 Pulmonary Function Tests

#### 5.1.19 Cardiac Stress Test

## 5.2 Procedures During Treatment

SABR treatment requires one week for planning and one week for delivery of the 1 or 3 fractionation schemes. HD IL-2 must begin within 84 hours of the last SABR fraction. Each course of HD IL-2 consists of two cycles of approximately two weeks each (12-14 IV infusions q8h followed by about 9 days of break) requiring a total of four weeks.

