#### 6.1.7 Progression-Free Survival

Progression-free survival (PFS) is defined as the duration of time from the date of registration to time of progression or date of death due to any cause.

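### Sections 5.5.3 and 4.5 conflict on whether patients without an IL-2 cycle stay in follow-up, and 11.3 names no survival population; read literally, 5.5.3 would bias OS and PFS upward.

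*Combined protocol and SAP*

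**What the plan says.** Section 5.5.3 states that "patients must be withdrawn from the trial and replaced if they failed to receive at least one cycle of HD IL-2". It names no exception for death, progression or toxicity. Section 4.5 says that subjects meeting a section 5.5 criterion come off therapy, "however will continue to be followed up as per protocol described above".

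Section 2.2.1 defines OS as the "time between date of registration and the date of death due to any cause". Section 6.1.7 says that PFS "is defined as the duration of time from the date of registration to time of progression or date of death due to any cause". TTP in 2.2.3 has the same origin but does not count deaths. Section 5.2.2 places registration before the first SABR fraction, and 5.2.4 places the first IL-2 cycle nominally at day 15-22, with a window of 7 days either way.

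Section 11.3 plans Kaplan-Meier estimates of OS and PFS, and a one-sample log-rank test against a published historical arm. It does not say which patients enter these analyses. Sections 6.1.1 and 6.2 define sets for response and safety only.

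On what a cycle is, section 4.2.1 gives IL-2 "every 8h for a total of up to 14 doses (considered as one cycle", with no minimum. Section 5.2 describes "12-14 IV infusions q8h followed by about 9 days of break".

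**The concern.** A site cannot obey both instructions. Section 5.5 itself separates leaving treatment with follow-up permitted (5.5.1) from ending both treatment and follow-up (5.5.2), so withdrawal from the trial in 5.5.3 can naturally be read as leaving the study.

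On that reading, a patient who dies or declines between registration and IL-2 is removed, and the next patient takes the place. The analysed cohort is then alive by construction for the first two to four weeks or so after time zero, and the removed patients' later deaths and progressions go unrecorded. If those patients do worse than the rest, the survival curve rises with no treatment effect. The comparison is with an external curve, so nothing inside the trial would reveal the shift. Section 1.4 says that OS, PFS and TTP could each help to justify a phase III trial. Follow-up not collected at the time may not be recoverable.

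**Working it through.** **The plan's own figures.** Section 11.2 gives the Simon design as 3/17, then 9/33. Exact binomial calculation with p0 = 0.23 and p1 = 0.368 gives type I error 0.1966, power 0.8053, probability of early termination 0.427 and expected sample size 26.16. A full search returns the same design as optimal. These figures stand and are not in question. The plan gives no operating figures for the survival test.

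**Inputs for the survival check.**
- From the documents: 33 analysed patients (11.2); the Study Summary's maximum of 38, used only as an upper limit, so at most 38 - 33 = 5 replacements. The documents do not say that the extra five are for replacement.
- Assumed: number replaced k = 1 to 5; historical median m = 18 months; 24 months' accrual plus 24 months' further follow-up; death hazard in replaced patients h = 2 to 4 times that of the others; a historical curve that covers all patients entered; superiority declared at z < -1.96. Section 11.3 states neither alpha nor sidedness.

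**Step 1, a landmark proportion.** If survival at some time is 60% in the 33 retained patients and all k replaced patients die before it, survival among all registered patients is 0.60 × 33/(33 + k). If the replaced patients survive half as often, it is (33 × 0.60 + k × 0.30)/(33 + k).

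| k | All die early | Survive half as often |
|---|---|---|
| 1 | 58.2% | 59.1% |
| 2 | 56.6% | 58.3% |
| 3 | 55.0% | 57.5% |
| 5 | 52.1% | 56.1% |

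Leaving them out overstates the landmark by about 1 to 8 percentage points.

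**Step 2, the one-sample log-rank test under no benefit.** Let d = k/(33 + k). Choose the retained patients' hazard λ so that the registered population has the historical median:

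(1 - d)·exp(-λm) + d·exp(-λhm) = 0.5.

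The apparent median in retained patients is ln 2/λ. The test is z = (O - E)/√E, with E from the mixture curve. For example, k = 5 and h = 4 give d = 5/38 = 0.132 and an apparent median of 21.6 months against a true 18. Results from 20,000 simulated trials per setting, with ranges over h = 2 to 4:

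| k | Apparent median (months) | False superiority, all registered | False superiority, after removal and replacement |
|---|---|---|---|
| 2 | 18.8-19.4 | 1.7% | 2.6-3.3% |
| 3 | 19.1-20.1 | 1.9% | 3.1-4.3% |
| 5 | 19.8-21.6 | 1.8-1.9% | 4.8-6.9% |

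**Step 3, sensitivity to prognosis.** A second model gives retained patients a one-month death-free lag, at least 36 months' follow-up, and 10% of registered patients replaced (33/0.9 = 36.7 registered, so about 4 replaced). If those replaced have a median OS of 3-6 months, false superiority is 4.7-5.7%. At 9-12 months it is 2.9-3.9%.

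**The case against.** The strongest reply is that 5.5.3 only refills the accrual count. Section 4.5 refers to section 5.5 by name and keeps those patients in follow-up, 4.4 follows subjects for ten years or until death, and within 5.5 only 5.5.2 expressly ends follow-up. The replacement clause is also attached to inability to comply, while progression and toxicity are separate items with no replacement wording. This is a coherent reading and, if it governs, nothing is lost. It does not remove the point: the opposite instruction is mandatory in its wording, and 11.3 does not settle which patients are analysed.

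Four stronger readings are tempting, and the documents do not support them.
- A reader might infer that the plan excludes these patients from OS, PFS and TTP. No section says so; the loss occurs only if 5.5.3 overrides 4.5.
- A reader might infer that many early progressions disappear. First on-study imaging is at week 8 (5.2.7), and 6.1 asks for a confirming scan more than 6 weeks later. Before IL-2, mainly clinical events such as fracture or cord compression (6.1.4.5, 6.1.4.6) could count. The progressions at risk are chiefly later ones in removed patients.
- A reader might take the 12-14 infusions in 5.2 as a threshold for withdrawal. It describes a schedule. What stands is that no section says how much of a cycle satisfies 5.5.3.
- A reader might assume 20% replacement, which in the Step 3 model with a median OS of 3-6 months gives 13-18% false superiority. That implies 33/0.8 = about 41 registered patients, above the stated maximum of 38.

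It is also fair that entry requires ECOG 0-1 and excludes life expectancy under 6 months, that patients may miss IL-2 for reasons unrelated to prognosis, and that the go/no-go rule in 11.2 uses response only.

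**Conclusion.** The conflict between 5.5.3 and 4.5 is real, and the missing survival population in 11.3 leaves it open. Literal use of 5.5.3 would bias OS and PFS in favour of the combination if the replaced patients fare worse. TTP is affected only through their lost progressions.

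The size is conditional. With 2 to 5 replaced, an 18-month historical median and 2 to 4 times the hazard, false superiority at a nominal one-sided 2.5% goes from about 1.7-1.9% to roughly 3-7%, and the apparent median from 18 to 18.8-21.6 months. It is smaller with fewer replacements or a prognosis nearer the others'. If the historical curve also covers treated patients only, which the documents do not show, much of the contrast goes. This is a modest bias in secondary endpoints, worth correcting because the remedy is simple and must be prospective. The sample size and the response rule in 11.2 need no change on this account.

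**What to change.** - Reconcile 5.5.3 with 4.5, so that a patient without an IL-2 cycle leaves protocol therapy but is followed for progression and survival under 4.4, unless consent to follow-up is withdrawn (5.5.2). Confine replacement to the response count.
- State in 11.3 that OS, PFS and TTP are analysed in all registered patients from registration, including any replaced for the response count.
- Report the number replaced, with reasons.
- State what counts as having received one cycle for the replacement rule, reconciling 4.2.1 with 5.2.

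The cost is a wording amendment and survival calls for a few patients. The reported OS and PFS may be slightly less favourable.

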## 6.0 Measurement of Effect

## 6.1 Antitumor Effect

For the primary endpoint, response and progression will be evaluated in this study using the new international criteria proposed by the Response Evaluation Criteria in Solid Tumors (RECIST) Committee [JNCI 92(3):205-216, 2000], which was also used by the two randomized trials of HD IL-2 being used as historic controls for this trial [35, 36]. The only change from RECIST v.1.1 being implemented in this study is a confirmation of new lesions or progressive disease (PD) by a second scan >6wks apart, based on the immune RECIST (irRC) criteria proposed by Wolchok. et. al that is appropriate for immune-related treatment response [91]. This is primarily because immune response often can take longer time as compared to chemotherapy before producing a radiographic response and during this time new lesions may arise which will eventually regress and if it were not for a second confirmation, these patients would be labeled to have failed therapy. In addition, the majority of mRCC responders to HD IL-2 usually produce a durable response (median response duration of 24 months), therefore, this change will not affect the outcome [35]. Additional criteria for bone lesions and clinical endpoints of pathologic fracture and cord compression are added to this study (see Section 6.1.4).

Changes in only the largest diameter (unidimensional measurement) of the tumor lesions are used in the RECIST v1.1 criteria outlined in http://www.recist.com/.

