While the exact mechanism of anti-tumor activity of HD IL-2 is unclear, seven phase II and multiple phase III trials have clinically proven the efficacy of IL-2 in inducing durable CR and PR in clear cell RCC patients. In contrast, molecularly targeted therapies fail to induce CR and do not cure patients. The reported RR for treatment with HD IL-2 (600,000-800,000 IU/kg q8h x 14 as tolerated) in multiple phase III trials ranges from 20% to 23.2% and the CR ranges from 7%-9% [34-36]. Among the patients who achieve CR, >80% remained disease free at last follow-up with a median survival over 10 years [34, 37, 38] suggesting a durable response or a cure of mRCC. Alternate schedules and decreased doses of IL-2 have been tried without any improvement in outcome [35, 36, 39]. Predictive immunologic markers would enormously aide clinicians in selecting patients who will respond to HD IL-2.

There is significant toxicity of HD IL-2 affecting multiple organ systems that requires ICU admission for the duration of administration. These side effects include hypotension, cardiac arrhythmias, metabolic acidosis, fever, nausea and vomiting, dyspnea, edema, oliguria and renal failure, neurotoxicity, and dermatologic complications including a mortality of up to 1. Alternate schedules and decreased doses of IL-2 have been tried without any improvement in outcome [35, 36, 39]. Predictive immunologic markers would enormously aide clinicians in selecting patients who will respond to HD IL-2 and spare the toxicity to those who will not.

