#### 6.1.4.3 Evaluation of Best Overall Response

The best overall response is the best response recorded from the start of the treatment until disease progression/recurrence (taking as reference for progressive disease the smallest measurements recorded since the treatment started). The subjects best response assignment will depend on the achievement of both measurement and confirmation criteria.

Target Lesions	Non- Target Lesions	New Lesions	Overall Response	Best Response for this Category
-------------------	---------------------------	-------------	---------------------	---------------------------------------

				Also Requires:
CR	CR	No	CR	≥4 wks. confirmation
CR	Non- CR/Non- PD	No	PR	> 4 wks. confirmation
PR	Non-PD	No	PR	
SD	Non-PD	No	SD	documented at least once ≥4 wks. from baseline
PD	Any	Yes or No	PD	
Any	PD*	Yes or No	PD	no prior SD,
Any	Any	Yes	PD	PR or CR
* In exceptional circumstances, unequivocal progression in non-target lesions may be accepted as disease progression.				

Note: Subjects with a global deterioration of health status requiring discontinuation of treatment without objective evidence of disease progression at that time should be reported as "*symptomatic deterioration*". Every effort should be made to document the objective progression even after discontinuation of treatment.

Note: If subjects respond to treatment and are able to have their disease resected, the patient's response will be assessed prior to the surgery.

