#### 11.2 Sample Size and Accrual

The previous studies show that the maximum RR for mRCC patients treated with HD IL-2 is 23% [35]. We expect a >60% improvement in this rate leading to a 36.8% RR for mRCC patients when treated with SABR and IL2. The calculation of the sample size is based on the RR and Simon's optimal two-stage design will be used with  $(\alpha,\beta)=(0.20, 0.20)$  [120]. The RR of 23% is set as the lowest desirable rate and 36.8% is the rate we are targeting. We chose type I error of 0.20 and type II error of 0.20. That is, if the true response rate is less than 23%, the probability of wrongly accepting the treatment for further study is 20%, and if the true response rate exceeds 36.8%, the probability of wrongly rejecting it for further study is 20%. According to the optimal two-stage design, a maximum of 33 patients will be needed. In the first stage, 17 patients will be evaluated. If 3 or fewer responses are observed, then the trial will be terminated for futility. Otherwise an additional 16 patients (second stage) will enter the trial. Finally, if more than 9 responses are observed among 33 patients, then the regimen

(SABR+IL-2) may be considered as the experimental arm of a Phase III trial. The average sample size for this phase II trial is 26.2 patients, and the probability of early termination is 0.43 for a drug with response probability of 23%.

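### The 23% null comes from trials scored by RECIST, while parts of this plan score response only after progression is confirmed; the 20% false-go rate holds only if HD IL-2 alone yields at most about 23.1% under this trial's scoring.

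*Combined protocol and SAP*

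**What the plan says.** **Benchmark.** Section 11.2: "The RR of 23% is set as the lowest desirable rate and 36.8% is the rate we are targeting". The 23% is described there as the highest RR in earlier HD IL-2 studies. Section 1.3 says that the reported RR "in multiple phase III trials ranges from 20% to 23.2% and the CR ranges from 7%-9" percent. Section 6.1 cites RECIST (2000) for the primary endpoint, "which was also used by the two randomized trials of HD IL-2 being used as historic controls for this trial".

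**Change made here.** Section 6.1 then makes one change to RECIST 1.1 for this trial: new lesions or progressive disease (PD) must be confirmed by a second scan more than 6 weeks later. Its rationale is that new lesions may appear early under immunotherapy and later regress, and "if it were not for a second confirmation, these patients would be labeled to have failed therapy". It adds that HD IL-2 responses are durable (median 24 months), "therefore, this change will not affect the outcome". Sections 2.4.1 and 2.4.3 also name immune-related criteria for response and require progression to be verified at least 6 weeks later.

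**Text pointing the other way.** Objective 2.1.1 measures RR by RECIST 1.1 and mentions no modification. Section 6.1.4.1 allows no new lesions in a CR or PR. The 6.1.4.3 table scores target-lesion PD, or any new lesion, as PD with no confirmation step.

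**Response window.** Section 6.1.4.3: "The best overall response is the best response recorded from the start of the treatment until disease progression/recurrence".

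**Decision rule.** Section 11.2: stop if 3 or fewer of 17 respond; otherwise go if more than 9 of 33 respond, with type I and type II error of 0.20 each. Section 11.3 plans no analysis of RR by unmodified RECIST.

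**The concern.** In a single-arm trial the null rate is the only comparator for the go decision, so it has to be measured by the same rule as the endpoint. Best overall response is collected until progression. If progression counts only after confirmation, the window stays open longer. A patient whose target sum rises 20% at week 8 and later falls at least 30% below baseline has progressed under the benchmark's rule, but can be a PR under the confirmation rule. The opposite reclassification cannot occur through this rule, so its effect on RR is zero or upward.

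The defence in 6.1 addresses a different quantity. Duration of response describes patients who have already responded. It does not say how many patients with early, unconfirmed progression go on to respond.

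At stake is whether part of an apparent gain over IL-2 alone comes from scoring rather than from adding SABR, and whether the 20% error rate in 11.2 describes the rule that will be applied.

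**Working it through.** **1. Which rule applies to which patient.**

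| Early event | 6.1, 2.4.3 | 2.1.1 | 6.1.4.1 | 6.1.4.3 table |
|---|---|---|---|---|
| Target sum up 20%, later reverses | PD only if confirmed | PD at first scan (no modification stated) | Unclear: the verification clause may cover new lesions only | PD, no confirmation shown |
| New lesion, later regresses | PD only if confirmed | PD at first scan (no modification stated) | PD needs verification, but no new lesion is allowed in CR or PR | PD, no confirmation shown |

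The sections disagree in both rows. Target growth that reverses is the clearest route to an extra responder, because the new-lesion route is barred by the CR and PR definitions.

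**2. Reproduce the plan's figures.** Inputs from 11.2: n1 = 17, r1 = 3, n = 33, r = 9, p0 = 0.23, p1 = 0.368. With X ~ Bin(17, p) and Y ~ Bin(16, p):

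- P(early stop) = P(X ≤ 3)
- P(go) = Σ over x = 4 to 17 of P(X = x) · P(Y ≥ 10 − x)
- E(N) = 17 + 16 · [1 − P(early stop)]

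At p = 0.23, P(early stop) = 0.427 and E(N) = 17 + 16 × 0.573 = 26.2, against a stated 0.43 and 26.2. P(go) = 0.197, within the 0.20 cap. At p = 0.368, P(go) = 0.805. A grid search for the Simon optimal design returns 3/17 and 9/33. The arithmetic in 11.2 is correct.

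**3. Slack in the error rate.** Solving P(go) = 0.20 gives p = 0.2309. The margin above the 23% null is 0.09 percentage points of RR.

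**4. P(go) by the HD IL-2 rate under the scoring actually used.** The rule is unchanged. The size of the shift is an assumption, since the documents give none.

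| HD IL-2 RR as scored here | P(go) |
|---|---|
| 20% | 0.099 |
| 23% | 0.197 |
| 24% | 0.237 |
| 25% | 0.281 |
| 26% | 0.327 |

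A 3-point rise in the true rate corresponds to 0.03 × 33 ≈ 1 extra expected responder in 33.

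**5. The same question as a share f of non-responders reclassified.** RR as scored = p0 + f(1 − p0).

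| f | Standard-RECIST rate 23% | Standard-RECIST rate 20% |
|---|---|---|
| 1% | RR 23.8%, P(go) 0.227 | RR 20.8%, P(go) 0.121 |
| 3% | RR 25.3%, P(go) 0.295 | RR 22.4%, P(go) 0.174 |
| 5% | RR 26.9%, P(go) 0.368 | RR 24.0%, P(go) 0.237 |

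From 23%, 1% reclassified already exceeds 0.20. From 20%, a 3-point shift lands on 23% and gives 0.197; a 4-point shift gives 0.237.

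**The case against.** A reader might infer that the 20% type I error is already broken. The documents do not support that. They give no size for the shift, and 23% is the top of the 20% to 23.2% range in 1.3, so the null may contain slack of its own. This stands, and the result is therefore conditional. It does not remove the point, because 11.2 defines its 20% error at 23%, where there is almost no room.

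A reader might also infer from the rationale in 6.1 that patients whose new lesions regress will be counted as responders. Sections 6.1.4.1 and 6.1.4.3 bar that, and 6.1 does not describe reversible target growth. Even the target-growth route depends on 6.1 and 2.4.3 prevailing over the 6.1.4.3 table and 2.1.1. This also stands. What is certain is that the scoring rule is unsettled, and that one of its readings is more lenient than the benchmark.

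The net direction of the whole scoring system is not established either. Sections 6.1.4.5 and 6.1.4.6 add pathologic fracture away from treated sites and cord or cauda equina compression as progression, with no second scan, and these can close the response window earlier. The one-way argument covers the confirmation rule alone.

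Finally, the change is disclosed with a reason, alpha is deliberately loose, and a go only makes the regimen a candidate for a Phase III trial. These facts lower the stakes. They do not make the durability argument answer the question.

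**Conclusion.** The point holds in conditional form. By the plan's own account, the 23% and the confirmed-PD version of RR rest on different progression rules. The confirmation rule can only keep or raise RR, and the claim of no effect is unsupported. The stated 20% false-go rate is valid if HD IL-2 alone gives at most about 23.1% under the scoring finally used. At 24%, 25% and 26% the false-go chance is 0.237, 0.281 and 0.327.

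This rests on three assumptions: that the historical trials were scored as 6.1 says, which cannot be checked from the documents; that the confirmation rule governs at least target-lesion growth; and that the shift lies in the range shown, which is illustrative. It does not show that the error rate is in fact above 20%, and it finds no fault in the sample-size calculation.

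**What to change.** Reconcile 2.1.1, 2.4.1, 2.4.3, 6.1, 6.1.4.1 and 6.1.4.3 and name one RECIST version. State in 6.1 and 11.2 that the stage-1 (3/17) and final (9/33) counts use best overall response by RECIST without the PD-confirmation modification: the first scan meeting PD ends the response window, and later shrinkage earns no credit. Report RR with confirmed-PD scoring alongside as a supportive result, and say there whether the bar on new lesions in CR and PR still applies. Delete the statement that the change leaves the outcome unaffected.

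The cost is protocol wording and a second scoring of the same scans, with no new data. The decision RR may be slightly lower than the confirmed-PD RR. Treatment and scanning while PD is being confirmed are unchanged. The fix removes the confirmation mismatch only; any difference between RECIST versions would remain.

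The alternative, keeping confirmed-PD scoring for the decision and raising the null, is dearer. With the target held at 36.8% and both errors at 0.20, the Simon optimal design becomes 3/16 and 12/43 for a 24% null, 5/22 and 15/53 for 25%, and 6/25 and 18/62 for 26%, and the documents offer no basis for choosing among them.
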